5.2. ADS-5102 for Walking Impairment in Multiple Sclerosis

Amantadine has been reported to possess multiple pharmacological activities. The precise mechanism through which amantadine may exert its beneficial effects in MS has not been completely elucidated, and multiple pharmacological activities may contribute to amantadine's effects in this indication. Amantadine is known to be a low affinity, uncompetitive inhibitor of the N-methyl-D-aspartate (NMDA) receptor (Kornhuber et al., 1991; Bresink et al., 1995; Parsons et al., 1995, Parsons et al., 1996). Nonclinical studies have demonstrated that amantadine decreases neuronal toxicity associated with excessive glutamate release (Danysz et al., 1997) and improves cognitive function (Wang et al., 2014). Amantadine has been shown to increase the action potential duration in rat atria to a similar degree as dalfampridine (Northover, 1994), which suggested that amantadine may also block potassium channels. Studies conducted by Adamas with amantadine in rat coronal brain slices demonstrated that amantadine blocked neuronal potassium channels over a wide concentration range (10-1000 μ M). Blockade of potassium channels is the putative mechanism by which dalfampridine is believed to exert its clinical benefit in MS walking (Ampyra package insert). In addition, amantadine has been shown to modulate cholinergic signaling (Albuquerque, et al., 1978), affect serotonin levels (Wesemann et al., 1979), inhibit microglial activation, and increase the release of glial cell-derived nerve growth factor (Ossola et al., 2011).

Adamas conducted a Phase 2 study of ADS-5102 in MS patients, Study ADS-AMT-MS201, to assess the safety and tolerability of ADS-5102 in patients with MS. Secondary objectives were to assess the potential benefit of ADS-5102 on walking speed, functional mobility, walking distance, fatigue, depression, and cognition of patients with MS. Walking speed was prespecified as the key secondary outcome, and trial participants were screened for the presence of walking impairment on the basis of performing the Timed 25-Foot Walk (T25FW) test in 8 to 45 seconds, inclusive.

This 4-week, placebo-controlled, proof-of-concept study showed a manageable safety and tolerability profile for ADS-5102 in participants with MS. The safety data were similar to the previously published results in Parkinson's disease (PD) (Pahwa et al., 2015; Pahwa et al., 2017). The types of AEs reported were also consistent with the known safety profile of immediate-release amantadine.

A statistically significant effect on the percent change in walking speed from baseline was observed and a greater proportion of ADS-5102-treated participants experienced a $\geq 20\%$ improvement. Trends suggesting benefit, which did not reach statistical significance, were observed for the Timed Up and Go (TUG) test, and less so on the 2-Minute Walk Test (2MWT). Previous studies indicate these tests are less sensitive, requiring longer follow-up and larger sample size to demonstrate benefit (Hobart, 2017). Results on participant-reported walking ability, measured by the MSWS-12 over 4 weeks, did not demonstrate benefit. The short duration of the study may not have provided sufficient time to detect a treatment effect on this patient-reported outcome, as the recall period for the questionnaire is 2 weeks.

The goal of the Phase 3 study, ADS-AMT-MS301, is, therefore, to confirm the efficacy, safety, and tolerability of ADS-5102 as a treatment to improve walking in the patients with MS that was suggested in the Phase 2 study.

5.3. Product (Formulation) Rationale

The ADS-5102 investigational drug product is a capsule containing ER coated pellets of amantadine HCl. The rationale for a formulation that slows the release of amantadine is based upon the nature and timing of the CNS side effects associated with immediate release (IR) amantadine relative to dosing, as well as observations with other CNS active drugs. Immediate release formulations of amantadine HCl have a short t_{max} of 2-4 hours (Aoki and Sitar, 1988), and the most commonly reported side effects are CNS-related, including dizziness (lightheadedness), agitation, hallucinations, and insomnia, which can occur within a few hours of dosing (Jackson et al., 1967; Hayden et al., 1981). The AEs reported with amantadine therapy in MS (Murray, 1985; Canadian MS Research Group 1987; McEvoy et al., 1987; Rosenberg and Appenzeller, 1988; Chiba et al., 1992; Krupp et al., 1995; Ashtari et al., 2009; Berger, 2011) are overall similar to those observed with amantadine treatment in PD. The increased frequency of AEs at higher doses, in particular CNS events and sleep disturbances, limits the routine use of amantadine IR at doses of 300 mg/day or higher. The pharmacologic rationale for improved tolerability of an ER formulation of amantadine is that the reduction in the rate of rise in plasma concentration may reduce the CNS adverse effects.

Recent preclinical experiments have shown that the rate of rise in amantadine plasma concentrations may contribute to CNS impairment, with a more rapid rise in plasma concentrations resulting in greater CNS impairment. Studies conducted by Adamas have demonstrated that rapid bolus infusion with amantadine resulted in greater CNS impairment, as

determined by time balancing on a rotating rod (Rotarod, a validated model of safety pharmacology in rodents), whereas as a slower rate of infusion reaching the same final plasma concentration produced no discernible CNS side-effects. These results are consistent with favorable tolerability profile of ADS-5102 as demonstrated in clinical studies supporting the dyskinesia indication in patients with Parkinson's disease.

5.4. Dose Selection

Two dosages of ADS-5102 are being tested in Study ADS-AMT-MS301, 137 mg/d and 274 mg/d, to adequately characterize the dose-response curve.

The 274 mg dose was selected because this was the dose that was tested in the Phase 2 study, Study ADS-AMT-MS201, and showed a statistically significant effect on walking speed in the T25FW test. Additionally, the 274 mg dose showed a clearly positive trend toward significance in the TUG test in the Phase 2 study. With respect to the safety and tolerability of the 274 mg dose, the overall AE profile and the AE-related dropout rate observed in Study ADS-AMT-MS201 support entering Phase 3 in MS, with the preliminary expectation that acceptable safety and tolerability will be confirmed. The AE profile was qualitatively similar to the AE profile discernible from the published studies of amantadine IR in MS ([Canadian MS Research Group 1987](#); [Chiba et al., 1992](#); [Krupp et al., 1995](#); [Ashtari et al., 2009](#); [Berger, 2011](#)) and to the AE profile observed in the clinical studies of ADS-5102 in PD, as reflected in the GOCOVRI™ prescribing information.

Although the 137 mg dose was not evaluated as a separate treatment arm in the Phase 2 study, the data suggest that this dose may confer some effect on walking speed. A separation in the least squared (LS) mean walking speeds between the ADS-5102 and placebo groups was evident at the first post-baseline T25FW test, which was performed after 2 weeks of dosing. As the first 2 weeks of dosing constituted a 1-step titration, with subjects in the active-therapy arm receiving ADS-5102 at 137 mg/d for the first week, it is plausible that the time spent at the 137 mg dose could have contributed to the efficacy signal at study Week 2. The low dropout rates during the first week of dosing suggest that the 137 mg dose is tolerable. Even if the 137 mg dose of ADS-5102 should prove to be only minimally effective, it could still provide a valuable alternative to patients who may be intolerant of a higher dose of amantadine.

5.5. Dosing Regimen and Titration

ADS-5102 is to be taken once daily at bedtime. The t_{max} for ADS-5102 is expected to occur at 12 to 14 hours post dose. ADS-5102 is designed to maintain high concentrations throughout most of the waking day, with concentrations decreasing in the evening. This pharmacokinetic profile could enable higher daily doses to be tolerated with a once-nightly ER preparation than are typically reported for dosing with an amantadine IR formulation. The once daily at bedtime dosing regimen may also provide enhanced convenience and improve compliance.

The 12-week Double-Blind Treatment Period of the study includes a 2-step, forced titration phase for subjects randomized to the 274 mg/d ADS-5102 arm of the study, followed by a maintenance phase of approximately 10 weeks. The titration occurs over approximately the first 2 weeks of the study, with dosing in the first week at 137 mg/d, and in the second week at 205.5 mg/d. Subjects randomized to the 137 mg/d arm will undergo a sham titration, but will, in fact, be continuing on a daily dose of 137 mg/d throughout the titration and maintenance periods. Similarly, subjects randomized to the placebo arm of the study will undergo a sham titration, but

will, in fact, be continuing on placebo throughout the titration and maintenance periods. The sham titrations are included to preserve blinding. No down-titration will be permitted.

Although it is anticipated that the slow absorption of the ER formulation will facilitate the ability of patients to tolerate higher dose of amantadine than historically reported as use in MS, the titration phase is being included for the 274 mg dose to further ensure its tolerability. When a 1-step forced titration, from 137 to 274 mg, was employed in Adamas' clinical studies of ADS-5102 in PD, premature discontinuation rates were still higher during the earlier, as compared to the later, times on-study. Moving from a 1-step to a 2-step titration should serve to further limit early discontinuation of study drug.

5.6. Rationale for ADS-AMT-MS301 Study Design

The overall objectives of this Phase 3 study are to establish the efficacy of ADS-5102, an ER form of amantadine, in improving walking performance, and to characterize its safety and tolerability at a dosage of 137 or 274 mg/d, administered once daily at bedtime, in MS patients with walking impairment. A multicenter, 3-arm, randomized, placebo-controlled, double-blind, parallel-group study, incorporating a Single-Blind Placebo Run-In Period prior to randomization and forced up-titration for the high-dose group, is an appropriate design to accomplish these objectives.

The duration of the Double-Blind Treatment Period of the study, 12 weeks, should be adequate to demonstrate an effect of ADS-5102 on walking ability, as a positive effect on walking was observed after 4 weeks of treatment in the Phase 2 study. Obtaining serial efficacy measures at multiple timepoints throughout the 12-week duration should indicate whether any observed effect is diminishing, increasing, or holding steady over time. If, as in PD, a positive effect is observed with active study drug early after its initiation, and the effect holds relatively constant through to the last efficacy assessment, then it is likely that the 12-week duration will be assessed to have been adequate to establish the durability of the drug effect over time.

Incorporating into the study design a Single-Blind Placebo Run-In Period for all eligible subjects prior to randomization to their assigned treatment group in the double-blind phase of the study provides several potential advantages over starting double-blind treatment immediately following the initial screening period. By allowing subjects the opportunity to discontinue treatment while only receiving placebo, AEs related to study participation, but not to study drug, per se (e.g., AEs related to anxiety about receiving an experimental therapy), in subjects who might be prone to experiencing such AEs, may be reduced in the safety and tolerability data obtained by study's end and provide a truer reflection of the drug's safety and tolerability profile. Also, it is generally believed that for many outcome measures, the durability of the placebo response diminishes over time. The addition of the pre-randomization placebo run-in period provides additional time for any potential contribution of a placebo response to have decreased by the time of the final efficacy evaluation. Lastly, by performing efficacy assessments during the placebo run-in period, the impact of practice effects on the variability of efficacy measures can be diminished.

The duration of the Single-Blind Placebo Run-In Period, 4 weeks, is considered long enough to permit realization of its potential benefits without being so long as to substantially increase the overall burden of study participation. It is also consistent with the duration of the placebo run-in periods employed in other drug studies in walking impairment in MS ([Goodman et al., 2009](#); [Goodman et al., 2010](#)).

As amantadine is not currently known, or widely held, to be a disease modifying treatment for MS, i.e., is generally considered to be a symptomatic therapy, no irreparable harm is considered likely to result from withholding the experimental treatment in the subjects randomized to receive placebo.

5.7. Population to be Studied

Subjects with MS who are experiencing impaired walking will be randomized into the study.

6. TRIAL OBJECTIVES AND PURPOSE

6.1. Primary Objective

- To evaluate the efficacy of 274 mg ADS-5102 in subjects with multiple sclerosis (MS) with walking impairment as measured by the Timed 25-foot Walk (T25FW, feet/second) at Week 16

6.2. Secondary Objectives

6.2.1. Key

- To evaluate the efficacy of 274 mg ADS-5102 in subjects with MS and walking impairment as measured by the T25FW, Timed Up and Go (TUG) test, and the 2-Minute Walk Test (2MWT) at Week 16.
- To evaluate the efficacy of 137 mg ADS-5102 in subjects with MS and walking impairment as measured by the T25FW, the TUG test, and the 2MWT at Week 16.

6.2.2. Supportive

- To evaluate the efficacy of 274 mg ADS-5102 and 137 mg ADS-5102 in subjects with MS and walking impairment as measured by the T25FW, the TUG, and the 2MWT across all study visits.
- To evaluate the efficacy of 274 mg ADS-5102 and 137 mg ADS-5102 in subjects with MS and walking impairment as measured by the Multiple Sclerosis Walking Scale-12 (MSWS-12) in subjects treated with 274 mg ADS-5102 and subjects treated with 137 mg ADS-5102.

6.2.3. Safety

- To evaluate the safety and tolerability of 274 mg and 137 mg of ADS-5102 in subjects with MS and walking impairment.

7. INVESTIGATIONAL PLAN

7.1. Overall Study Design

This is a multicenter, 3-arm, randomized, placebo-controlled, double-blind, parallel-group study of ADS-5102 (amantadine ER capsules) in MS subjects with walking impairment, incorporating a Single-Blind Placebo Run-In Period prior to randomization, and forced up-titration for the high-dose group.

All subjects will have received a stable regimen of MS medications, both disease modifying and symptomatic, for at least 30 days prior to screening, and will continue the same doses and regimens for the duration of their study participation, to the extent compatible with good neurological care. Subjects will not have used amantadine, dalfampridine, or any 4-AP or 2,4-diaminopyridine (2,4-DAP) preparation within 30 days prior to screening.

Consented subjects who complete the up to 3-week screening period will undergo a 4-week Single-Blind Placebo Run-In Period during which they will administer placebo as 2 capsules once daily at bedtime.

Subjects who complete the Single-Blind Placebo Run-In Period and continue to meet study eligibility criteria will be randomized with equal probability to 1 of 3 treatment groups: placebo or ADS-5102 at a final dosage of either 137 or 274 mg/d (treatment groups are identified by their final dosage). Study drugs will be administered as 2 capsules once daily at bedtime.

Subjects who are randomized to placebo will receive placebo capsules throughout the 12-week Double-Blind Treatment Period, including the 2-week forced titration and 10-week maintenance phases.

Subjects who are randomized to 137 mg of ADS-5102 will receive 137 mg of ADS-5102 throughout the 12-week Double-Blind Treatment Period, including the 2-week forced titration and 10-week maintenance phases.

Subjects who are randomized to 274 mg of ADS-5102 will receive 137 mg for the first week (Week 1 of the forced titration phase of the Double-Blind Treatment Period), 205.5 mg for the second week (Week 2 of the forced titration phase of the Double-Blind Treatment Period), and 274 mg for the remaining 10 weeks of the 12-week Double-Blind Treatment Period.

Subjects will return to the clinic for safety and efficacy assessments at Week 0 and Week 2 prior to randomization and at Weeks 4 (randomization and baseline visit), 6 (only safety), 8, 12, and 16 after randomization. In addition, telephone visits for safety assessments will be conducted at Weeks 5 and 7. Subjects who withdraw from the study before Week 16 will have an early termination visit that includes safety follow-up and efficacy assessments, as appropriate.

Subjects who complete 12 weeks of double-blind treatment (16 weeks total treatment, including placebo run-in) without significant protocol deviations, as assessed by the investigator and the sponsor, will be eligible to enter an optional open-label extension (OLE) study, protocol ADS-AMT-MS303. The Week 16 visit of Study ADS-AMT-MS301 will serve as the first study visit of Study ADS-AMT-MS303 for those subjects who consent to participate.

Subjects who complete 12 weeks of double-blind treatment (16 weeks total treatment, including placebo run-in) but elect not to participate in the OLE study will return to the clinic for a final

post-treatment safety and efficacy assessment 2 weeks after their Week 16 visit (Week 18), i.e., after being off treatment for approximately 2 weeks.

The End of Study (EOS) is defined as when a subject completes the Week 16 visit (if electing to enter the OLE study) or the Safety Follow-Up Visit (if electing not to enter the OLE study).

All study visits and efficacy assessments should be scheduled at approximately the same time of day for an individual subject. To the extent practicable, study visits and efficacy assessments should be scheduled to occur when a subject is not likely to be experiencing acute side effects from a concomitant medication (e.g., flu-like side effects following interferon-beta injection).

Efficacy assessments should be conducted in following sequence: MSWS-12; T25FW; TUG; 2MWT. Subjects using an assistive device during the walking assessments at Screening should use the same assistive device for all subsequent walking tests. Each efficacy assessment for an individual should be performed by the same clinical rater, if possible.

Adverse events and concomitant medications will be recorded beginning with the first dose of study drug and continuing through the last study visit.

The schedule of assessments is provided in [Appendix A](#).

7.2. Number of Subjects

Approximately 570 subjects are to be enrolled in the Single-Blind Placebo Run-In Period at approximately 80 study sites to ensure that 540 subjects complete the Single-Blind Placebo Period and are eligible to be randomized into the Double-Blind Treatment Period (approximately 180 enrolled in each treatment group: placebo, 137 mg ADS-5102, and 274 mg ADS-5102).

7.3. Treatment Assignment

Consented subjects who complete screening, meet study eligibility criteria, and complete the Single-Blind Placebo Run-In Period will be randomized with equal probability to 1 of the 3 treatment groups to receive placebo, 137 mg ADS-5102, or 274 mg ADS-5102.

7.4. Dose Adjustment Criteria

7.4.1. Dose Adjustment for Renal Impairment

Subjects whose estimated glomerular filtration rate (eGFR) falls below 60 mL/min/1.73 m², confirmed by repeat testing, should discontinue study drug (see [Section 8.5](#)).

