18. Presence of orthostatic hypotension at screening: a decrease in systolic blood pressure (at least 20 mm Hg) or diastolic blood pressure (at least 10 mm Hg) within 3 minutes of the subject standing up, compared to pressures obtained while sitting
19. Any laboratory test results outside of the central laboratory's normal range at screening that are assessed by the investigator to be clinically significant. Documentation by the investigator of clinical significance or insignificance must accompany out of range laboratory test results at screening
20. Aspartate aminotransferase (AST) and/or alanine aminotransferase (ALT) screening laboratory results > 2 times the upper limit of normal
21. Estimated glomerular filtration rate (eGFR) < 60 mL/min/1.73 m² (per Modification of Diet in Renal Disease [MDRD] calculation)
22. Inability to swallow oral capsules, or a history of gastrointestinal malabsorption that would preclude the use of oral medication
23. If female, is pregnant or lactating
24. If a sexually active female, is not surgically sterile or at least 2 years post-menopausal, or does not agree to utilize a highly effective hormonal method of contraception (an IUD, or vasectomized male partner is also acceptable), in combination with a barrier method, from screening through at least 4 weeks after the completion of study treatment. If a sexually active male, does not agree to utilize condoms from screening through at least 4 weeks after the completion of study treatment.
25. Received live attenuated influenza vaccine within 2 weeks prior to randomization or planning to receive live attenuated influenza vaccine during the duration of the study (amantadine may interfere with the efficacy of live attenuated vaccine)

26. Current treatment with medications that may affect urinary pH: carbonic anhydrase inhibitors, sodium bicarbonate, urinary acidification agents, quinine, quinidine, triamterene, or trimethoprim
27. Treatment with an investigational drug or device within 30 days prior to screening
28. Treatment with an investigational biologic within 6 months or 5 half-lives, whichever is longer, prior to screening
29. Current participation in another clinical trial
30. Prior or current participation in an Adamas clinical trial
31. Planned elective surgery, with the exception of minor dermatological procedures, during study participation

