8.5. Discontinuation of Study Drug

Subjects should discontinue study drug if judged necessary by the investigator or sponsor, and reasons may include any of the following:

- eGFR falls below 60 mL/min/1.73 m², confirmed by repeat testing (see [Section 7.4.1](#))
- Need to take a medication that is excluded or that may interfere with study measurements

- Subjects requiring MS treatment adjustment due to disease exacerbation or progression should be discussed with one of the Medical Monitors
- Intolerable or unacceptable AEs
- Positive pregnancy test

Subjects who discontinue study drug will be encouraged to complete the study. If the subject decides to withdraw from the study, he or she will have an early termination visit that includes efficacy assessments and safety follow-up.

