11.2. Clinical Laboratory Tests

The clinical laboratory and other tests relating to safety to be performed during the study are described in the following table. The estimated total blood volume collected throughout the study (for clinical laboratory tests) is expected to be approximately 30 mL for safety serum chemistry and hematology laboratory evaluations.

Table 6: Clinical Laboratory and Other Assessments

Assessment	Study Visit	Description
Hematology	Screening Week 16 (or ET)	Blood samples (5 mL) will be collected. Hematology parameters include: hemoglobin, hematocrit, mean corpuscular volume (MCV), mean corpuscular hemoglobin concentration (MCHC), red blood cell (RBC) count, white blood cell (WBC) count, WBC differential count, and platelet count. Hematology will be conducted by a central laboratory.
Serum Chemistry	Screening Week 16 (or ET)	Blood samples (10 mL) will be collected (fasting is not required). Routine serum chemistry parameters include alkaline phosphatase, albumin, blood urea nitrogen, calcium, carbon dioxide, chloride, creatinine, γ -glutamyl transferase, glucose, inorganic phosphorus, potassium, alanine aminotransferase, lactate dehydrogenase, aspartate aminotransferase, sodium, total bilirubin, and total protein.
Urinalysis	Screening Week 16 (or ET)	Urinalysis will be performed using sponsor-supplied dipsticks, including leukocytes, specific gravity, pH, protein, ketones, glucose, nitrite, blood, urobilinogen, and bilirubin. If nitrite, blood, or protein tests are positive, a microscopic examination will be performed.
Serum pregnancy test (if applicable)	Screening Week 16 (or ET) Safety Follow-Up	Serum pregnancy test will be performed for all female subjects of childbearing potential.
Urine pregnancy test (if applicable)	Week 0, Week 2 Baseline/Week 4	Urine pregnancy test will be performed for all female subjects of childbearing potential.

Estimated glomerular filtration rate (eGFR) will be calculated by the central laboratory using MDRD.

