12.1. Screening/Day -21 to -1

During screening, potential subjects for the study will be fully informed about the nature of the study and possible AEs. Subjects who wish to participate in the study must read and understand the consent form and sign the document after the investigator has answered all questions to the candidate’s satisfaction. Further procedures can begin only after the consent form has been signed.

The screening visit must be conducted within 21 days prior to the Week 0 visit. Potential study subjects will be evaluated for entry into the study according to the stated inclusion and exclusion criteria. Individuals who are identified during this screening as not eligible for study enrollment need not complete all screening procedures. The reason for ineligible status is to be documented.

The following procedures will be performed to establish each subject’s qualifications for enrollment into the study:

- The subject is fully informed about the study and gives written informed consent to participate in the study
- Confirm commitment of caregiver and/or study partner, if applicable
- Review inclusion/exclusion criteria and evaluate initial subject eligibility
 - Administer the EDSS (administration instructions and forms will be provided separately)
 - Administer the screening T25FW (administration instructions and forms will be provided in the study manual)
- Record demographic information

- Medical history with an emphasis on the subject's MS and walking impairment, and past treatments for these conditions; alcohol and drug use, other neurological diseases, psychiatric disorders including Major Depressive Disorder or symptom (e.g., hallucinations, agitation, paranoia, suicidal ideation), history of seizures, stroke or TIA; history of MI or congestive heart failure (CHF); and history of cancer
- Record all medications currently taken or taken in the previous 30 days
- Complete physical examination
- Obtain subject weight in kilograms and height in centimeters
- Vital signs (blood pressure, respiratory rate, heart rate, and temperature), including assessment of orthostatic hypotension
- Blood sample for central laboratory analysis including hematology, serum chemistry and eGFR
- ECG (12-lead)
- Urinalysis
- Blood sample for serum pregnancy test in females of childbearing potential.
- Administer the C-SSRS (administration instructions and forms will be provided in the study manual)

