12.8. Double-Blind Treatment Period: Week 16 Visit

- Assess and record concomitant medications
- Assess and record AEs
- Complete physical exam
- Vital signs (blood pressure, respiratory rate, heart rate, and temperature)
- Obtain subject weight in kilograms
- Blood sample for central laboratory analysis including hematology, serum chemistry, and eGFR
- Urinalysis
- Blood sample for serum pregnancy test in females of childbearing potential
- Efficacy assessments
- C-SSRS
- Collect used/unused blister cards and evaluate compliance

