13.1.8. Follow-up of Adverse Events and Serious Adverse Events

All AEs and SAEs must be followed until resolution (or return to baseline status), or until the condition stabilizes or is otherwise explained, or until the subject dies or is lost to follow-up. The investigator is responsible for ensuring that follow-up includes any supplemental investigations

as may be indicated to elucidate as completely as practical the nature and/or causality of the AE/SAE. This may include additional laboratory tests or investigations, histopathological examinations, or consultation with other health care professionals.

The sponsor may request that the investigator perform or arrange for the conduct of supplemental measurements and/or evaluations. If a subject dies during participation in the study or during a recognized follow-up period, the investigator should provide the sponsor with a copy of any post-mortem findings, including histopathology.

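### SAP Table 3, the only planned by-arm chemistry count, has no eGFR criterion, so most falls below the protocol's limit of 60 go uncounted; two of its low flags can never be met

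*Combined protocol and SAP*

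**What the plan says.** **The limit of 60.** Exclusion criterion 21 (protocol 8.2) bars entry below 60, "per Modification of Diet in Renal Disease [MDRD] calculation". Protocol 7.4.1, repeated in SAP 4.1, says that a subject below 60, "confirmed by repeat testing, should discontinue study drug". Protocol 8.5 lists the same event among possible reasons for stopping, under a conditional opening: "Subjects should discontinue study drug if judged necessary by the investigator or sponsor".

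**The data.** Under protocol 11.2, eGFR "will be calculated by the central laboratory using MDRD". Chemistry is scheduled at Screening and at Week 16 or early termination (Table 6, Appendix A). The Week 16 list (12.8) includes "Blood sample for central laboratory analysis including hematology, serum chemistry, and eGFR", and the early termination list (12.9) has the same item.

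**The analysis.** In the SAP text available, eGFR appears only in the abbreviation list and Section 4.1. SAP 10.2.2 plans a by-arm count of potentially clinically significant (PCS) chemistry changes as defined in Table 3. That table has rows for creatinine and blood urea nitrogen (BUN) but none for eGFR. A value counts only if it meets both the observed-value and the change criterion:

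- Creatinine high: above 2.0 x ULN and a rise above 100%.
- Creatinine low: below 0.3 x LLN and a decrease above 100%.
- BUN low: below 0.2 x LLN and a decrease above 100%.

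**The concern.** The protocol treats 60 as the renal boundary for both entering the trial and staying on drug, and the central laboratory supplies the values. A safety reader would therefore expect to see how many subjects in each arm started at or above 60 and ended below it. No planned table shows this. A reader who turns to the PCS table instead may take an empty creatinine row to mean that renal function held up, when the criterion responds only to severe falls. The two low flags are a separate slip: an empty row there carries no information, because nothing could fill it.

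**Working it through.** The plan states no figure for this point, so there is none to reproduce. The check asks how far eGFR must fall before the creatinine flag is met, and then what the missing count could show.

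**1. Fall in eGFR needed for the change criterion.** The documents name MDRD but do not print the equation. Assumption: eGFR varies as creatinine to the power -k, with k from 1.0 to 1.2.

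- Fall when creatinine doubles = 1 - 2^(-k): 50.0% (k = 1.0), 56.5% (k = 1.2).
- Entry eGFR at which doubling lands exactly on 60 = 60 x 2^k: 120 (k = 1.0), 137.8 (k = 1.2).

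Anyone entering between 60 and those values is already below 60 before the change criterion is met. The observed-value criterion (2 x ULN) is required as well, so it can only delay the flag. The result therefore does not depend on the laboratory's ULN.

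**2. Example from an entry eGFR of 90.**

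- Fall needed to reach 60: 1 - 60/90 = 33.3%.
- eGFR when creatinine has doubled: 90 x 2^(-k) = 45.0 (k = 1.0) or 39.2 (k = 1.2).
- A fall to 50 needs a creatinine rise of (90/50)^(1/k) - 1 = 80% (k = 1.0) or 63% (k = 1.2). Both are short of 100%, so there is no flag.

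**3. The low flags.** Percent decrease = 100 x (baseline - value)/baseline. With value at or above 0 this cannot exceed 100%. A decrease above 100% needs a negative concentration. Since both criteria must hold, neither low flag can ever be met.

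**4. Age of the comparison value.** Protocol 12.1 states: "The screening visit must be conducted within 21 days prior to the Week 0 visit". Randomization is at Week 4 (day 28). Chemistry is not scheduled in between, so under SAP 5.4 the baseline is the Screening value, which is 28 + 1 = 29 to 28 + 21 = 49 days old at randomization, ignoring visit windows.

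**5. Precision of the missing count.** With 0 crossings among 180 tested, the exact two-sided 95% upper limit is 1 - 0.025^(1/180) = 2.0%.

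**6. Chance crossings.** Assumptions: true eGFR T is unchanged, and values are log-normal with a within-subject CV of 5% to 8%. With s = sqrt(ln(1 + CV²)), the chance that a single Week 16 value is below 60 is Phi(ln(60/T)/s):

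| True eGFR T | CV 5% | CV 8% |
|---|---|---|
| 62 | 25.6% | 34.1% |
| 65 | 5.5% | 15.8% |
| 70 | 0.10% | 2.7% |
| 75 | 0.00% | 0.26% |

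Chance crossings come almost wholly from subjects near the entry limit and are expected in every arm.

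**The case against.** **No promise is broken.** Protocol 14.5 commits to tabulating PCS laboratory changes without fixing the cut-offs, and neither document makes eGFR an endpoint or says that each stopping criterion gets a table. This stands, and it is why the point is minor.

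**Other outputs may show cases.** Reasons for premature discontinuation are tabulated by arm (SAP 6.1), clinically significant laboratory findings become adverse events (protocol 13.2.1), and there are alert flags (SAP 10.2), listings and mean changes (protocol 14.5). This stands in part. None of these is a by-arm count against 60. SAP 6.1 names no eGFR category. A fall first found at Week 16, when dosing ends, cannot be a reason for premature discontinuation. Out-of-range values are not adverse events in themselves.

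**The proposed count is not the stopping event.** The rule requires confirmation; the count would use one scheduled value, and near 60 some crossings are noise. This stands in full and must be said on the table.

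**Stronger readings that the documents do not support:**

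- A reader might infer that the dosing rule in 7.4.1 is itself wrong or cannot operate. The rule acts on any eGFR obtained, and event-driven testing is allowed: of adverse event follow-up, protocol 13.1.8 says "This may include additional laboratory tests or investigations, histopathological examinations, or consultation with other health care professionals". An asymptomatic fall between Screening and Week 16 could go unseen, but whether to add visits is a clinical choice, not an error shown here.
- A reader might infer from protocol 5.3 that the high-dose arm will have more off-schedule renal tests. That passage concerns central nervous system and sleep events on immediate-release amantadine and says nothing of renal testing.
- A reader might discount the 180 by the 20% dropout ceiling in SAP 5.2. Dropouts are not thereby untested: the early termination visit includes eGFR.

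**Conclusion.** The point holds as a minor gap in safety reporting, located in SAP 10.2.2. Table 3 generally does not count subjects whose eGFR falls below 60, because its creatinine high flag waits for a fall of roughly half or more. That size rests on the assumed exponent of 1.0 to 1.2; the absence of an eGFR criterion and the two impossible low flags rest on the text alone. How many subjects are affected is unknown. It would go too far to say that renal decline would be invisible, or that the new count would measure how many subjects met the stopping rule.

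**What to change.** In SAP 10.2.2:

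1. Add one descriptive by-arm table on the Safety set: the number tested at Screening and at Week 16 or early termination; the number and percent with eGFR of at least 60 at Screening and below 60 at the later test (Week 16 and early termination also shown separately); and the number with no later test. Footnote that these are single unconfirmed values, that they include chance crossings near 60, and that they are not the confirmed stopping event.
2. Replace the two low-flag change criteria (creatinine and BUN) with attainable ones, or with N/A, as Table 3 already does for ALT, AST, gamma-glutamyl transferase and total bilirubin.

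The cost is one table from data already collected and two corrected cells, with no new visit, procedure or protocol amendment. The drawback is that the count is descriptive only and includes some noise near the entry limit.
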